### 6.4.4.3 UVA Cancer Center DSMC Reporting Requirements

All adverse events must be reported into the University of Virginia Cancer Center OnCore database within the time frame specified below:

	Grade 1	Gra	ade 2		Grade 3 Grade 4 & 5					
	Expected and	Expected	Unexpected	Expe	ected	Unexp	pected	Expected	Unexpected	
	unexpected		·	Without hospitalization	With hospitalization	Without hospitalization	With hospitalization		•	
Unrelated Unlikely	Not required	Not required	Not required	OnCore 30 days	OnCore 15 days	OnCore 30 days	OnCore 15 days	OnCore 15 days	OnCore 15 days	
Possible Probable Definite	OnCore 30 days	OnCore 30 days	OnCore 15 days	OnCore 30 days	OnCore 15 days	OnCore 15 days	OnCore 15 days	OnCore 15 days	OnCore (24-hrs)* 7 days	

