## 6.0 TRIAL FLOW CHART

## 6.1 Study Flow Chart

# 6.1.1 Arm 1

Trial Period:	Pre- Study	Treatment		Post-treatment		Survival
Visit:	Screening	CRT	Pembro	EOT visit 	Imaging	Follow-
Scheduling Interval:	-42d-1d	W1-W8	W9-W15	35 ± 5d	12w ± 10d post-CRT	Up 
Administrative Procedures						
Informed Consent/ IE	Х					
Demographics/Medical History	Х					
Concomitant Medication Review	Х					
Disease Status						Х
Survival Status						Х
Study Treatments						
Cisplatin		Х				
Radiation		Х				
MK-3475 administration			x 			
Specimen Collection						
Tissue Collection 	Х	x 			Х	
Research Blood Collection	Х	X 			Х	
Clinical Procedures/ Laboratory Assessments						
Pregnancy Test (Urine or Serum) 	х					
Review Adverse Events	Х	Х	Х	Х		

<sup>1 All subjects should be followed for 5 years following treatment to monitor disease status and overall survival. There are no per protocol assessments, all subjects should be monitored according to the standard of care of the treating physicians.

<sup>2 Each subject should return to the clinic for a visit 30-40 days following the last study treatment (of either pembrolizumab or chemoradiation) for assessment of adverse events

<sup>3 Pembrolizumab treatment should be scheduled for every 21 days ( $\pm$  3 days) starting on Week 9.

<sup>4 Fresh tissue biopsies are required. If archival tissue is available these may also be submitted to supplement fresh tissue collected at baseline.

<sup>5 Tissue and blood specimen collected during CRT interval should be obtained at  $5 \pm 2$  weeks

<sup>6 Women of childbearing potential must have a negative pregnancy test within 72 hours of first dose of study treatment.

Trial Period:	Pre- Study	Treat	tment	Post-tre	Survival		
Visit:	Screening	CRT	Pembro	EOT visit 	Imaging	Follow-	
Scheduling Interval:	-42d-1d	W1-W8	W9-W15	35 ± 5d	12w ± 10d post-CRT	Up 	
Physical Examination/ECOG	X7	X 	X 	х	X 		
Vital Signs	Х	Х	Х	Х			
PT/INR and aPTT 	Х						
CBC with Differential 	Х	x 	X 	Х			
Serum Chemistry Panel 	Х	X 	X 	Х			
Thyroid panel 	Х		X 	Х			
	Tumor Imaging/Disease Assessments						

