Pregnancy Test (Urine or Serum) 	х				
Review Adverse Events	Х	Х	Х		
Physical Examination/ECOG	X 	X 	х	X 	
Vital Signs	Х	Х	Х		

<sup>1 All subjects should be followed for 5 years following treatment to monitor disease status and overall survival. There are no per protocol assessments, all subjects should be monitored according to the standard of care of the treating physicians.

<sup>2 Each subject should return to the clinic for a visit 30-40 days following the last study treatment (of either pembrolizumab or chemoradiation) for assessment of adverse events

<sup>3 Pembrolizumab treatment should be scheduled for every 21 days ( $\pm$  3 days) starting on Day 1.

<sup>4 Fresh tissue biopsies are required. If archival tissue is available these may also be submitted to supplement fresh tissue collected at baseline.

<sup>5 Tissue and blood specimen collected during CRT interval should be obtained at  $5 \pm 2$  weeks

<sup>6 Women of childbearing potential must have a negative pregnancy test within 72 hours of first dose of study treatment.

<sup>7 Physical exam at screening and at the time of the post-treatment imaging should include a clinical tumor assessment

<sup>8 Physical exams should be done at a minimum every 3 weeks during study treatment interval

Trial Period:	Pre- Study	Treatment	Post-tre	eatment	• • •
Visit:	Screening	CRT + MK-3475	EOT visit 	Imaging	Survival Follow-
Scheduling Interval:	-42d-1d	W1-W9	(35 ± 5d)	12w ± 10d post-CRT	Up 
PT/INR and aPTT 	Х				
CBC with Differential 	Х	x 	Х		
Serum Chemistry Panel 	Х	X 	Х		
Thyroid panel 	Х	X 	Х		
Tumor Imaging/Disease As	sessments				
MRI 	Х				
PET/CT 	Х			Х	

<sup>9 Prior to first day of treatment (Day 1 Week 1), laboratory tests do not need to be repeated if screening labs were performed within 14 days prior to treatment date.

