#### 6.4 Assessing and Recording Adverse Events

Adverse events should be collected from the start of treatment through a minimum of 30 days following the last study treatment.

After informed consent has been obtained, and prior to initiation of investigational treatment, only serious adverse events caused by a protocol-mandated intervention should be reported (e.g., serious adverse events related to invasive procedures such as biopsies).

**After initiation of study treatment**, all adverse events will be reported according to the guidelines in the following sections. Throughout the study, investigators should report any deaths, serious adverse events, or other adverse events of concern that are believed to be related to the investigational intervention.

An adverse event is defined as any untoward medical occurrence in a patient or clinical investigation subject administered a pharmaceutical product and which does not necessarily have to have a causal relationship with this treatment. An adverse event can therefore be any unfavorable and unintended sign (including an abnormal laboratory finding, for example), symptom, or disease temporally associated with the use of a medicinal product or protocol-specified procedure, whether or not considered related to the medicinal product or protocol-specified procedure. Any worsening (i.e., any clinically significant adverse change in frequency and/or intensity) of a preexisting condition that is temporally associated with the use of pembrolizumab, is also an adverse event.

Adverse events may occur during the course of the use of Pembrolizumab in clinical trials or within the follow-up period specified by the protocol, or prescribed in clinical practice, from overdose (whether accidental or intentional), from abuse and from withdrawal.

Table 6. Adverse Event Reporting Overview						
Event Type	Collection Timeframe	Reporting Timeframe	Reference			
Routine Adverse Events	the start of treatment through at	Within 30 days to UVa	Section 6.4			
Serious Adverse Events†	least 30 days following the last study treatment	Within 24h to UVa	Section 6.4.4.1			
Events of Clinical Interest	the start of treatment through 90 days following the last dose of pembrolizumab (or date subject starts new cancer treatment)	Within 24h to UVa	Section 6.4.4.2			
Overdose	On pembrolizumab dosing days	Within 24h to UVa	Section 6.4.2			

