## 6.4.1.3 Attribution

The Principal Investigator will evaluate all AEs and assess their toxicity and attribution, if any, to pembrolizumab. See Table 8 for further guidance on evaluation of attribute. The following criteria will define the attribution:

**Definite:** The AE is clearly related to the investigational intervention. **Probable:** The AE is likely related to the investigational intervention. **Possible:** The AE may be related to the investigational intervention. **Unlikely**: The AE is doubtfully related to the investigational intervention. **Unrelated**: The AE is NOT related to the investigational intervention.

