### 7.1 Evaluation Criteria

## 7.1.1 Safety Endpoints

All patients receiving any protocol treatment will be evaluated for safety. Safety assessments will include:

- i. Incidence and severity of adverse events.
- ii. Incidence of dose limiting toxicities (DLT) defined in section 7.4.

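### The OnCore table exempts Grade 1-2 events not attributed to pembrolizumab, contradicting its own lead sentence and Table 6; if required OnCore entries feed the AE tables, low-grade incidence during CRT is not comparable between arms

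*Combined protocol and SAP*

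**What the plan says.** Section 6.4.4.3 begins: "All adverse events must be reported into the University of Virginia Cancer Center OnCore database within the time frame specified below". The table that follows has two attribution rows. In the Unrelated/Unlikely row, the Grade 1 cell and both Grade 2 cells (expected and unexpected) say that entry is not required. In the Possible/Probable/Definite row, the same three cells require entry in 30, 30 and 15 days. Grades 3 to 5 are required in both rows.

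The attribution that selects the row is to one drug. Section 6.4.1.3 says: "The Principal Investigator will evaluate all AEs and assess their toxicity and attribution, if any, to pembrolizumab". No separate attribution to cisplatin or radiation is provided for. The flow chart footnotes schedule pembrolizumab "starting on Week 9" in Arm 1 (Section 6.1.1) and "starting on Day 1" in Arm 2 (Section 6.1.2).

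The general rule in Section 6.4 is broader: "Adverse events should be collected from the start of treatment through a minimum of 30 days following the last study treatment". Table 6 gives routine events a reporting time of "Within 30 days to UVa", with no limit by grade or attribution. Section 6.4.5.1 has the DSMC review every adverse event. Section 6.4 also says that, once treatment has started, "all adverse events will be reported according to the guidelines in the following sections", and Section 6.4.4.3 is one of those sections.

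The first safety endpoint in Section 7.1.1 is "Incidence and severity of adverse events". No data source is named there, and no grade limit is set.

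**The concern.** The row a low-grade event falls into depends on attribution to pembrolizumab, and during CRT only one arm has received pembrolizumab. The same Grade 1 nausea or Grade 2 diarrhoea in Week 4 can be a required record in Arm 2 but hardly in Arm 1. The trial is open label, so the person rating attribution knows the arm.

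Safety is the second primary objective (Section 3.1). Arm 1 in Weeks 1-8 is CRT alone, and so is the trial's only randomized reference for what concurrent pembrolizumab adds to acute toxicity. If the entry rule decides which low-grade events reach the analysis, that reference is lost for Grades 1-2, and each arm's own low-grade incidence is too low.

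Separately, a site cannot tell from the text which rule governs: the lead sentence and Table 6, or the cells of the OnCore table.

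**Working it through.** The plan states no figure on this point, so there is none to reproduce. The check sets the sections side by side and then illustrates the consequence.

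**Step 1: which Grade 1-2 events must be entered in Weeks 1-8.**

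| | Arm 1 (CRT alone) | Arm 2 (CRT plus pembrolizumab) |
|---|---|---|
| Exposed to pembrolizumab | No | Yes, from Day 1 |
| Can be rated at least Possible | Essentially no; Table 7 makes exposure and time course part of the assessment | Yes |
| Grade 1-2, Unrelated/Unlikely | Entry not required | Entry not required |
| Grade 1-2, at least Possible | Essentially does not arise | Entry required |
| Grade 3-5, any attribution | Entry required | Entry required |

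The arms differ in one line of the table: Grade 1-2 events rated at least Possible.

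**Step 2: whether Section 6.4 overrides the table.** Table 6 asks for routine events of any grade and attribution. But Section 6.4 hands the detail to the sections that follow it, and Section 6.4.4.3 is the only one with a grade-by-attribution rule. Both readings are open, so the conflict is real.

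**Step 3: whether the stopping rule is affected.** A DLT (Section 7.4.1) must be at least possibly related to pembrolizumab. Every DLT therefore falls in the row where entry is required at all grades. The within-arm boundary is untouched.

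**Step 4: illustration.** The documents give neither the incidence of Grade 1-2 CRT toxicity nor the share rated at least Possible. Both are assumptions here. Let p be the true proportion of patients with a given Grade 1-2 toxicity in Weeks 1-8, equal in both arms. Let a be the proportion of those patients in whom it is rated at least Possible. Then

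proportion with a required record = p × a.

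With p = 0.80:

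- Arm 1, a = 0: 0.80 × 0 = 0%.
- Arm 2, a = 0.25: 0.80 × 0.25 = 20%.
- Arm 2, a = 0.50: 0.80 × 0.50 = 40%.
- Arm 2, a = 0.75: 0.80 × 0.75 = 60%.

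The apparent difference is 20 to 60 percentage points when the true difference is zero. Both arms are understated: Arm 1 by 80 points, Arm 2 by 80 − 60 = 20 to 80 − 20 = 60 points.

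Over a wider range, p from 0.50 to 0.90 and a from 0.10 to 0.75, Arm 2 runs from 0.50 × 0.10 = 5% to 0.90 × 0.75 = 67.5%, about 2 to 30 of 44 patients. Arm 1 stays at 0 of 44. If entry did not depend on attribution, both arms would show the same p.

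**The case against.** A reader might infer that the reporting rule fixes adverse event incidence by arm, so that Arm 2 is bound to show more low-grade toxicity. The documents do not support that, for four reasons.

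- Nothing says that OnCore entries are the analysis dataset. Section 6.4.4.3 is headed as a DSMC reporting requirement. Other routes carry no such filter: Table 6, the medical record (Section 6.4.1), the AE case report forms or worksheets mentioned in Section 6.4.4.2, and the investigator's duty in Section 9.4 to enter all required data on the case report forms.
- Arm 2 events are not all required. Those rated Unrelated or Unlikely are exempt there too, and an exemption does not forbid entry.
- Grade 3-5 entry does not depend on attribution. No between-arm test of adverse events is planned. Section 7.0 disclaims definitive comparisons between arms, although in the immunologic context.
- The percentages rest on assumed inputs. High attribution shares may be doubtful, since Table 7 asks whether another drug explains the event and Section 5.5.1 separates immune-related from CRT diarrhoea.

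A reader might also infer that the DSMC would miss Grade 2 immune-related events, the grade at which the immune-related toxicity table in Section 5.3.2.1 starts to act for several organs. That is too strong. An event managed as immune-related would ordinarily be rated at least Possible, and so must be entered. Events of clinical interest are also reported within 24 hours (Section 6.4.4.2). What remains is Grade 2 events judged Unlikely.

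All of this stands and makes the point conditional. It does not remove the contradiction in the text. Nor does it ensure even capture, because a site that follows the table as written may omit these events, and voluntary entry across several open-label sites need not be uniform.

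**Conclusion.** Two things hold without any assumption. First, the OnCore table contradicts its lead sentence, Table 6 and the DSMC remit. Second, its requirement for Grade 1-2 events in Weeks 1-8 differs by arm, because attribution is to pembrolizumab only and the arms start it at different times.

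One thing holds conditionally. If the AE tables are built from required OnCore entries, Grade 1-2 incidence during CRT is too low in both arms and cannot be compared between them. Section 7.1.1 leaves that condition open by naming no source.

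The size cannot be derived from the documents. The 0% versus 20-60% contrast shows what the rule could do under assumed inputs and does not estimate the bias. Grade 3-5 incidence and the DLT boundary are not affected. The point should be corrected because it touches a primary safety endpoint and is cheap to repair.

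**What to change.** In Section 6.4.4.3, reconcile the table with its lead sentence, Table 6 and Section 6.4.5.1. Require OnCore entry of Grade 1-2 events within 30 days in both arms whatever the attribution, from the start of treatment to the end of the AE window. The existing 15-day time for unexpected, related Grade 2 events can stay. At minimum, require all Grade 2 events.

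In Section 7.1.1, name the source of the AE analysis and state that incidence is tabulated by arm, regardless of attribution.

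If the entry rule is kept, limit by-arm incidence drawn from OnCore to Grade 3 and above, and say so.

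The cost of the main change is one table row and extra data entry for events that Section 6.4.1 already places in the medical record. The fallback needs no extra entry but loses the low-grade detail of a primary safety endpoint, so it is the weaker choice.

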### 6.4.4.4 IRB Reporting Requirements

Serious and unexpected adverse events must be submitted to the site Institutional Review Board according to the participating site institutional policies.

### 6.4.4.5 Reporting to the FDA

The Sponsor-Investigator for the study (the UVA PI or designee) is responsible for providing safety updates to the FDA per the following guidelines. The reporting times refer to the time the Sponsor-Investigator received knowledge of the AE.

UVa PI HELD IND							
Type of Event	To whom will it be reported:	Time Frame for Reporting	How reported?				
Life-threatening and/or fatal unexpected events related or possibly related to the use of the investigational agent.	FDA	Within 7 calendar days of the study team learning of the event	Form FDA 3500A (MedWatch) or narrative				
Serious, unexpected and related or possibly related adverse events	FDA	Within 15 calendar days after the study team receives knowledge of the event	Form FDA 3500A (MedWatch) or narrative				
All adverse events	FDA	Annually	IND annual report				

Table 8. FDA Reporting Requirements

#### 6.4.4.6 Reporting to Participating Sites

The Sponsor-Investigator for the study (the UVA PI or designee) is responsible for providing safety updates to all participating sites per the following guidelines:

Table 9. Required Reporting to Participating Sites

UVA PI of MULTI-SITE TRIAL							
To whom will it be Time Frame for							
Type of Event	reported:	Reporting	How reported?				

Serious, unexpected and related or possibly related adverse events	All Research Sites	Within 15 calendar days after the Overall PI receives knowledge of the event	IND/IDE Safety Report (Cover letter, copy of MedWatch/narrative)
Unanticipated Problem	All Research Sites	Within 15 calendar days from the time the Overall PI receives knowledge of the event.	Letter to Participating PIs, Copy of MedWatch or narrative

### 6.4.5 Data Safety Monitoring Plan

The Data and Safety Monitoring Board for this study is the UVA Data Safety Monitoring Committee (DSMC).

### 6.4.5.1 UVA Cancer Center Data Safety Monitoring Committee

The University of Virginia Cancer Center Data and Safety Monitoring Committee (DSMC) will provide oversight of the conduct of this study. The CC DSMC will report to the UVA Protocol Review Committee (PRC). The DSMC will review the following:

- All adverse events
- Audit results
- Application of study designed stopping/decision rules
- Whether the study accrual pattern warrants continuation/action
- Protocol violations

The CC DSMC will meet every month for aggregate review of AE data. Tracking reports of the meetings are available to the PI for review. Issues of immediate concern by the DSMC are brought to the attention of the PI (and if appropriate to the PRC and IRB) and a formal response from the PI is requested. Per the Cancer Center NIH approved institutional plan this study will be audited approximately every 6 or 12 months.

## 7.0 STATISTICAL CONSIDERATIONS

This is a randomized phase II study to assess the safety of CRT in combination with pembrolizumab given as consolidation therapy or current with CRT, and to obtain preliminary estimates of the immunologic effect of the addition of pembrolizumab to CRT in this patient population. Eligible participants will be randomized 1:1 between the two arms. All participants receiving any protocol treatment will be evaluated for safety and the primary immunologic endpoint which is the ratio of the phenotype of HPV-specific CD8+ T cells to regulatory T cells (CD8+/Treg). Patterns of change in other immunologic endpoints assessed in the tissue and blood will be estimated along with 90% confidence intervals. The purpose is not to make definitive comparisons between arms but to obtain preliminary estimates of change in CD8+ T-cells and regulatory T cells over time for the different treatment schedules.

Arm 1: pembrolizumab after completion of CRT Arm 2: pembrolizumab concurrent to CRT

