### 7.1.2 Immunologic Endpoints

All eligible patients for which the required follow-up tissue and blood samples are obtained will be evaluated for the difference in pre and post-CRT samples; difference in pre and during CRT samples; and difference in during CRT and post-CRT samples:

- i. ratio of CD8+ T cells to Tregs
- ii. HPV E2
- iii. E7 specific CD8+ T cells
- iv. regulatory FoxP3+ T cells (Tregs)

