## 7.2 Sample size and accrual

Results in Jordanova ES, et al 2008, report estimates of CD8+/Treg for normal cervix and cervical cancers tissue for cervical cancer patients who underwent radical hysterectomy with lymphadenectomy.[4] These data provide the assumed "natural baseline" of cancer patients' in this study with CD8+/Tregs being lower in cancer tissue, and results in a Cohen's *d*av effect size (ES) of 0.45. Estimated sample size is based upon being able to detect a similar effect size between CD8+/Tregs at baseline and end of CRT, and baseline to the 12 weeks post CRT assessment without correction for multiple comparisons. Data from Nilges, K et al, 2003, indicates a mean (standard deviation) of 23.32 (15.39) in CD8+/Tregs measured in the tumor infiltrating lymphocytes (TIL) from patients with cervical cancer. Given these data, 44 eligible patients are required (per arm) to assess change in pre/post CD8+/Tregs with an ES of 0.45 with type I and II errors of 10%. Each within arm comparison supports the following hypothesis. Cisplatin can kill T cells, therefore the CRT may eliminate both CD8+ HPV CTL and Tregs, and the ensuing or concurrent pembrolizumab treatment may increase the CD8+/Treg ratio (test that pembrolizumab will increase CD8+/Tregs to an ES of 0.45).

Adjusting for an overall 10% ineligibility/drop-out rate, maximum accrual to the study is estimated at 98 patients. Accrual is estimated at 4 patients a month, thus accrual to the study should be completed by 2.0 years with primary analysis at 3 years.

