#### 7.5 Analyses

The study is designed with sufficient power to assess pre/post change in immune measures with an ES of .45 within each arm and not to detect a predetermined difference in the changes overtime between the two arms. However, data from the study will be used to estimate; the magnitude of the difference in pre/post change for all parameters of interest between the two arms; as well as progression—free and overall survival. With 44 eligible patients per arm we have 67%, 75% and 87% power to detect an ES of 0.45, 0.5 and 0.6, respectively, for continuous immune parameters (normality assumed) with a 10% level t-test. With 44 patients the width of a 90% CI (exact Clopper-Pearson) around the complete metabolic response at 3 months of 70% and the distant metastases rate at 3 years of 20% are (57%, 81%) and (10%, 33%), respectively. Thus, any estimated rate outside of these bounds would be considered promising. For each arm, progression free survival (PFS) and overall survival will be estimated by the product-limit method of Kaplan and Meier along with 90% confidence bands. In patients with complete metabolic response at 3 months, 3-year PFS is 78% (Schwartz et al, 2007). This result will be used to guide interpretation of results on PFS from this study.

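### The plan gives two conflicting analysis sets for the primary CD8+/Treg endpoint, and the only one that can be computed is a complete-case set with no rule for missing samples

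*Combined protocol and SAP*

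**What the plan says.** Section 7.0 sets the population for the primary immunologic endpoint: "All participants receiving any protocol treatment will be evaluated for safety and the primary immunologic endpoint". Section 7.1.2, where the ratio is the first immunologic endpoint listed, sets a narrower one: "All eligible patients for which the required follow-up tissue and blood samples are obtained will be evaluated". Under that single population sentence it plans three comparisons: pre against post-CRT, then "difference in pre and during CRT samples; and difference in during CRT and post-CRT samples".

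Section 7.2 sizes the trial on eligible patients: "44 eligible patients are required (per arm) to assess change in pre/post CD8+/Tregs with an ES of 0.45". It then makes one allowance for all losses: "Adjusting for an overall 10% ineligibility/drop-out rate, maximum accrual to the study is estimated at 98 patients". Section 5.7.3 replaces only subjects who leave before receiving any treatment.

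Section 7.5 gives power, confidence intervals and Kaplan-Meier estimation. For the immune measures it names no analysis set, no method for missing samples and no sensitivity analysis.

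**The concern.** The two populations differ for treated patients later found ineligible and for treated patients without the required samples. Two analysts following the protocol could report different denominators for a primary objective. In an open-label trial the choice could also be made after the data are seen.

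A change score needs two samples, so the Section 7.0 set cannot be applied as written. In practice availability of samples decides who is analysed. The last sample is a fresh office biopsy 12 weeks after CRT (Section 6.3.4.2.1). Patients who stop for progression or toxicity move to follow-up, where only PFS and OS are named (Section 5.7.1). Those who withdraw consent are not followed at all (Section 5.7.2). If having the 12-week sample is related to the immune change, the estimated change is biased. If the all-samples reading is applied, usable pairs are also discarded.

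**Working it through.** **1. The sets side by side**

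| Treated patient | Section 7.0 | 7.1.2, literal | 7.1.2, per contrast |
|---|---|---|---|
| Eligible, all samples | in | in | in |
| Eligible, no 12-week sample | in | out of all three contrasts | in for pre/during only |
| Eligible, tissue but no blood at one visit | in | out of all three contrasts | out of contrasts using that visit |
| Found ineligible, all samples | in | out | out |

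**2. The plan's own figure.** Inputs from Section 7.2: effect size 0.45, type I and II errors of 10%. The sidedness is not stated there, and Section 7.5 says only "with a 10% level t-test". For a paired t-test, two-sided:

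- Normal approximation: ((1.645 + 1.282)/0.45)² = 42.3, so 43.
- Noncentral t: n = 44, power 90.2%. This matches the plan; one-sided would need 34.
- Inflation: 88/0.90 = 97.8, so 98, or 49 per arm.

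**3. Cost of the all-samples rule.** The documents give no sample-availability rate. Assumptions: every patient has a baseline sample; each of the two follow-up visits is lost independently with probability q; 49 per arm; no other losses. Patients with both follow-up visits number 49(1−q)². Patients with baseline and one given follow-up visit number 49(1−q).

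| q | All samples (power) | Available pairs, pre/during or pre/post (power) | Available pairs, during/post (power) |
|---|---|---|---|
| 10% | 39.7, about 40 (87.5%) | 44.1, about 44 (90.2%) | about 40 (87.5%) |
| 20% | 31.4, about 31 (78.9%) | 39.2, about 39 (86.8%) | about 31 (78.9%) |

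During/post needs both follow-up samples, so available pairs do not help it. If tissue and blood are both required and fail independently at each visit, the all-samples count is 49(1−q)⁴: about 32 (80.1%) at q = 10% and about 20 (61.6%) at q = 20%. That is an upper illustration, since tissue and blood will often be missed together.

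**4. Monotone loss.** If everyone who misses the on-CRT sample also misses the 12-week one, the patients with all samples are exactly the baseline/12-week pairs. The literal rule then costs the pre/post contrast nothing, and only pre/during loses patients.

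**5. Gain from a joint model.** Take the same losses and compound symmetry with an assumed correlation ρ of 0.3 to 0.7, among patients with a baseline and at least one later sample. Add the inverse covariance matrices over the observed patterns, invert to get Var(contrast), and set effective n = 2(1−ρ)/Var(contrast). Over available pairs, pre/post gains about 1.2 to 2.7 effective patients and during/post about 2.6 to 6.0.

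**6. Possible bias in a complete-case pair.** Assume a bivariate-normal selection model with correlation r between the change and having the sample, and a fraction m missing. The shift in the mean change, in SD units, is r·φ(Φ⁻¹(m))/(1−m).

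- m = 10%: r × 0.195, so 0.04 to 0.12 for r of 0.2 to 0.6.
- m = 20%: r × 0.350, so 0.07 to 0.21, which is 16% to 47% of the 0.45 target.

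With m = 20%, 39 pairs and no true change, entering that shift as the effect in the two-sided 10% t-test (SD unchanged) gives rejection in about 13% to 36% of trials. The direction depends on the sign of r.

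**The case against.** The strongest reply is that this is a wording matter. Section 7.0 is an overview, 7.1.2 is the operative endpoint section, and a change score exists only where samples exist. The treated-but-ineligible group should be small, because only eligible participants are randomised and eligibility packets are reviewed first (Section 6.3.1.2). The aim is preliminary estimation. Much of this stands, and it limits the point. It does not remove the conflict, and the within-arm change is the quantity on which the trial is sized.

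A reader might infer more than the documents support:

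- *That the plan necessarily analyses only patients with every sample.* Section 7.1.2 can be read contrast by contrast, which keeps a patient with baseline and on-CRT samples for that comparison.
- *That power falls to 84% to 75%.* Those figures come from taking losses out of 44 (36 to 28 patients). They ignore the inflation to 49 per arm in Section 7.2.
- *That available pairs help every contrast.* They do not help during/post.
- *That missingness is shown to depend on outcome.* It is plausible but inferred. The 12-week biopsy is mandatory and timed from completion of CRT, and nothing says that progression or response cancels it. That complete responders may yield no tumor is also inference.
- *That a completers analysis needs samples missing completely at random.* That is sufficient but not necessary. The mean change is unbiased whenever having the sample is unrelated to the change itself.

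**Conclusion.** The point holds as a conflict between Sections 7.0 and 7.1.2 on the set for a primary endpoint, with nothing in 7.2 or 7.5 to resolve it. Under either reading of 7.1.2 the analysis is complete-case.

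The loss of precision is modest to moderate. Under the stated assumptions the literal rule costs 2.7 to 7.9 points of power for pre/during and pre/post, nothing relative to available pairs for during/post, and less if losses are monotone. The possible bias could matter more, up to about half the target effect in the worst case shown, but it rests wholly on an assumed selection model.

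The stated sample size reproduces, so a reader who took this as a sizing error would be mistaken. The plan should be changed because the repair is cheap and the ambiguity concerns a primary endpoint.

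**What to change.** State one set in both Section 7.0 and Section 7.1.2: treated patients with a baseline and at least one later sample of the relevant type, saying explicitly whether treated-but-ineligible patients count. Apply the tissue and blood requirements separately to each marker, so that a missing blood tube does not remove a tumor measurement.

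In Section 7.5, analyse all available time points within each arm by a likelihood-based repeated-measures model and read the three contrasts from it. Prespecify the scale and the handling of zero counts. A log ratio is undefined at zero, and the plan itself anticipates zeros: Section 7.2 expects that CRT may eliminate both cell types, and Section 7.4.2 monitors for absence of CD8+ T cells. Say separately how a sample with no residual tumor is handled, since a model that fills in a ratio for tissue that does not exist answers a different question. Keep the completers analysis as sensitivity, and report missing samples by arm and reason.

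The cost is SAP wording and a standard model. Visits, 44 per arm and 98 in total are unchanged. The downside is that the model assumes samples are missing at random, so it does not cure bias when loss depends on the unobserved value.
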